8.3.3 Immediately Reportable Events

The investigator must immediately report (within 24 hours), using an IRE form, after he/she or site personnel become aware of any IRE (SAE, AE related to occupational exposure, UFIE, or confirmed pregnancy), by telephone, fax, or e-mail to the sponsor or designee using the contact information on the cover page of this protocol (please note that the IRE form is NOT the AE CRF). Patient confidentiality must be protected and contact information such as name, address, phone number or any other protected health information as determined by applicable local regulation must be redacted when forwarding Safety Information and supporting documentation. Details regarding the follow-up of IREs are included in Section 8.3.5.2.

8.3.4 Procedure for Breaking the Blind

This trial does not use blinding procedures.

8.3.5 Follow-up of Adverse Events

8.3.5.1 Follow-up of Nonserious Adverse Events

Nonserious AEs that are identified at any time during the trial must be recorded on the AE CRF with the current status (ongoing or resolved/recovered) noted. All nonserious events (that are not IREs) that are ongoing at the last scheduled contact will be recorded as ongoing in the CRF. For any AE having been identified throughout the trial, during analysis, additional relevant medical history information may be requested by the sponsor to further ascertain causality (including, but not limited to, information such as risk-related behavior, family history, and occupation).

8.3.5.2 Follow-up of Immediately Reportable Events

This trial requires that patients be actively monitored for IREs up to the Week 8/ET visit.

Immediately reportable events that are **identified or ongoing at the last scheduled contact** must be recorded as such on the AE CRF page and the IRE form. If updated information (eg, resolved status) on IRE status becomes available after a patient's last scheduled contact (up to last in-clinic visit for the entire trial), this must be reported to the sponsor and recorded on the AE CRF page and the IRE form, according to the appropriate reporting procedures described in Section 8.3.3.

It is expected that the investigator will provide or arrange appropriate supportive care for the patient and will provide prompt updates on the patient's status to the sponsor. The investigator will follow IREs until the events are:

- Resolved,
- Stabilized,
- The patient is lost to follow-up, or
- Has died.

Resolution means that the patient has returned to the baseline state of health and stabilized means that the investigator does not expect any further improvement or worsening of the patient's condition. The investigator will continue to report any significant follow-up information to the sponsor up to the point the event has resolved or stabilized, or the patient is lost to follow-up, or has died.

Refer to Section 10.2 for additional information regarding the follow-up period for patients that become pregnant or for pregnant partners of male patients.

8.3.5.3 Follow-up and Reporting of Immediately Reportable Events Occurring After Last Scheduled Contact

Any new IREs reported to the investigator which occur after the last scheduled contact and are determined by the investigator to be reasonably associated with the use of the trial drug, should be reported to the sponsor according to the procedures outlined in Section 8.3.3. This may include IREs that are captured on follow-up telephone contact or at any other time point after the defined trial period and continue to report any significant follow-up information to the sponsor until the events are resolved or stabilized, or the patient is lost to follow-up or has died.

9 Statistical Considerations

9.1 Sample Size

This is a single-arm trial to assess the effect of brexpiprazole on patient engagement in MDD patients through the following co-primary endpoints: 1) change from baseline to

Week 8 in IDS-SR-10-engagement; 2) change from baseline to Week 8 in IDS-SR Total score.

Based on the results of the appropriate brexpiprazole-plus-ADT arms from four previous Phase 2/3 brexpiprazole MDD trials, it is reasonable to expect a mean change of -2.5 (standard deviation = 6.5) in IDS-SR-10-engagement and a mean change of -5 (standard deviation = 13.5) in IDS-SR Total score from baseline to Week 8. A sample size of 100 completers (ie, patients who have an evaluation on IDS-SR Total score and IDS-SR-10-engagement at Week 8) will yield 95% power to show a difference from baseline in IDS-SR Total score and at least 95% power to show a difference from baseline in IDS-SR-10-engagement at a two-sided significance level of 0.05, respectively. It will ensure the overall power is at least 90%. After considering an ET rate of 25%, a total of 134 patients need to be enrolled in this trial.

9.2 Datasets for Analysis

The following analysis samples are defined for this trial:

Enrolled Sample: comprises all patients who signed an ICF for the trial and enrolled into the open-label treatment phase.

Safety Sample: comprises all enrolled patients who received at least one dose of open-label brexpiprazole.

Efficacy Sample: the Full Analysis Set comprises all patients in the Safety Sample who have a baseline value and at least one post-baseline efficacy evaluation for IDS-SR Total score and IDS-SR-10-engagement during the open-label treatment phase.

9.3 Handling of Missing Data

IDS-SR is utilized as the primary efficacy measurement to assess core diagnostic depressive symptoms as well as the atypical and melancholic symptom features of MDD. The IDS-SR consists of 30 items, all rated on a 0 to 3 scale with 0 being the "best" rating and 3 being the "worse" rating. Besides item 9, two sub-items 9A and 9B exist, with possible scores of 1, 2 or 3 for item 9A, and 0 or 1 for item 9B. The scores for these two sub-items are not included in the calculation of the total score. Item 11 or item 12 should be completed but not both, and similarly, item 13 or item 14 should be completed but not both. Should items 11 and 12 be rated both, then the maximum of the two scores will be used. The same approach will be used for handling items 13 and 14.

The IDS-SR Total Score is the sum of ratings of 28 item scores. The possible IDS-SR Total Score ranges from 0 to 84.

The IDS-SR-10-engagement is the sum of ratings of the selected 10 item scores, including item 8 - Response of your mood to good or desired events, item 15 - Concentration/decision making, item 16 - View of myself, item 17 - View of my future, item 19 - General interest, item 20 - Energy level, item 21 - Capacity for pleasure or enjoyment (excluding sex), item 22 - Interest in sex (please rate interest, not activity), item 23 - Feeling slowed down, and item 29 - Interpersonal sensitivity. The possible IDS-SR-10-engagement ranges from 0 to 30.

The mixed model repeated measure (MMRM) method assumes data are missing at random (MAR), which is a reasonable assumption in longitudinal clinical trials in MDD.¹⁵ However, the possibility of "missing not at random" (MNAR) data can never be ruled out. Sensitivity analyses based on MNAR will be performed and details will be provided in the SAP.

The observed cases (OC) data set will consist of actual observations recorded at each scheduled visit during the open-label treatment phase, and no missing data will be imputed. MMRM and sensitivity analyses based on MNAR will be performed on the OC dataset. The last observation carried forward (LOCF) approach will also be used to impute missing data for continuous and categorical efficacy endpoints. The LOCF data set will include data recorded at a scheduled visit during the open-label treatment phase or, if no observation is recorded at that visit, data carried forward from the previous scheduled visit at the open-label treatment phase. Baseline data will not be carried forward to impute missing values for the LOCF data set.

9.4 Statistical Analyses

9.4.1 Efficacy Analyses

9.4.1.1 Primary Efficacy Endpoint Analysis

The co-primary efficacy endpoints are as follows:

- 1) Change from baseline to Week 8 in IDS-SR-10-engagement.
- 2) Change from baseline to Week 8 in IDS-SR Total score.

The primary hypothesis is that the mean changes from baseline to Week 8 in both co-primary endpoints will differ from 0, separately. Each of the endpoints will be tested by fitting a MMRM analysis with an unstructured variance covariance structure at a two-sided significance level of 0.05 on OC dataset on Efficacy Sample. The model will include fixed effect terms for visit, baseline value, an interaction term of baseline value

by visit, and trial center. The trial will be claimed positive if both p-values are less than 0.05. Therefore, the overall type I error is controlled at 0.05 level.

In case there is a convergence problem with MMRM model with the unstructured variance covariance matrix, the following structures other than unstructured will be used in order of 1) heterogeneous Toeplitz, 2) heterogeneous autoregressive of order 1, and 3) heterogeneous compound symmetry and the first (co)variance structure converging to the best fit will be used as the primary analysis. If a structured covariance has to be used, the "sandwich" estimator of the standard error of the fixed effects parameters will be used in order to deal with possible model misspecification of the covariance matrix. Details will be provided in SAP.

One-sample Wilcoxon signed rank test will also be performed for each endpoint in case that the normality assumptions are violated.

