2.4 Trial Rationale

Currently, brexpiprazole is approved in Canada for use in adult patients for the treatment of schizophrenia and for the use as an adjunctive therapy to antidepressants for the treatment of MDD.

Post-marketing reports from various sources have revealed a clinical observation of brexpiprazole-treated patients, initially described as an increase or improvement in "engagement," "positivity," or "brightening." This unique effect was reported by physicians from multiple countries, and was also observed in reports received by the company call centers. Based on this spontaneous feedback, a post-hoc analysis of specific "engagement items" of the Inventory of Depressive Symptomatology Self-Report (IDS-SR) from the brexpiprazole pivotal trial data was conducted to explore patient ratings of this so-called "engagement effect," and patient interviews from previous MDD exploratory studies were analyzed for spontaneous use of "engagement" lexicon. Briefly, results indicated that MDD patients treated with adjunctive brexpiprazole demonstrated improvements vs adjunctive placebo on items that represented patient well-being and engagement. Furthermore, a majority of patients (~89%) that consented to participate in exit interviews after exploratory studies used language reflecting an improvement in at least one of four engagement domains (social, emotional, physical or cognitive). Canadian healthcare providers confirmed that improvement in engagement has been observed in Canadian MDD patients, with reports of patients experiencing "increased motivation," "improved anhedonia," "clarity of mind," and being "more engaged" indicating that further prospective investigation of this effect is warranted. Furthermore, interviews recently conducted with MDD patients support the relevance of the previously-identified IDS-SR items in the measurement of patient engagement.

3 Objectives

The primary objective of this trial is:

• To prospectively characterize the effect of brexpiprazole on the concept of engagement, by evaluating IDS-SR-10-engagement, and the IDS-SR Total score, in patients with MDD with a current depressive episode.

The secondary objectives of this trial are:

- To evaluate patients' impression of improvement of their depression symptoms over time.
- To explore the relationship between engagement and other clinical effects of brexpiprazole, such as improvement in depressive symptoms and functioning.

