4.1 Type/Design of Trial

This is a phase 4, multicenter, open-label, flexible dose trial designed to assess the effects of brexpiprazole (flexible dose; 0.5 to 2 mg QD) as adjunctive therapy to ADT in patients with MDD. This trial is being conducted in line with the Canadian Product Monograph.⁵

The trial will be organized as follows:

Screening Phase: The screening period of up to 14 days (Days -14 to -1) will begin when the informed consent form (ICF) is signed. The purpose of the screening period is to assess eligibility criteria at 1 or more visits (as necessary to complete screening assessments) and to washout prohibited concomitant pharmacotherapy, if applicable.

Open-Label Treatment Phase: Patients meeting all of the inclusion and none of the exclusion criteria will be enrolled at the baseline visit into an 8-week open-label treatment phase. The screening and baseline visits can occur on the same day if the patient meets all required enrollment criteria. During the open-label treatment phase, all patients will receive brexpiprazole (that is, adjunctive brexpiprazole as a flexible dose; 0.5 to 2 mg/day) and will continue on the stable dose of ADT that they were taking at screening. Patients will attend visits at Weeks 2, 4, and 8 during the open-label treatment phase. If any patient discontinues the trial early, every effort should be made to complete the Week 8/early termination (ET) evaluations.

Following the completion of all scheduled visits, patients will be asked if they are interested in taking part in an exit interview, which will be separate from trial assessments and should occur within 30 days of the Week 8/ET visit. This also applies to patients withdrawn prematurely from the trial.

A schematic of the trial design is presented in Figure 1.2-1.

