4.2 Scientific Rationale for Trial Design

The current clinical trial will be the first prospective investigation to further characterize the effect of brexpiprazole on patient engagement.

The engagement items of the IDS-SR (which were previously identified by clinicians and subsequently confirmed by MDD patients) will serve as one of the co-primary outcome

measures. The relationship between engagement and other outcomes of interest (such as functioning, and depressive symptoms) will be explored in order to further characterize this engagement effect. The majority of the clinical assessments to be used in this trial are patient-reported, which is aligned with current views that patient-reported outcomes are imperative to demonstrating the clinical effectiveness of MDD treatments.⁸

While the current trial is interventional, the trial design is intended to assess the effect of adjunctive brexpiprazole on MDD patients when administered in a real-world setting. The open-label nature of the trial, as well as the patient population, the timing of the visits, the clinical assessments used, and the dosing parameters are intended to mimic Canadian clinical practice as closely as possible. Patient diaries will assess the patient's clinical experience in a manner that is as non-invasive as possible.

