9.4.1.2 Control of Experiment-wise Type I Error

Each of the co-primary endpoints will be tested by fitting a MMRM analysis at a two-sided significance level of 0.05 on OC dataset on Efficacy Sample, and the trial will be claimed positive if both p-values are less than 0.05. Therefore, the overall type I error is controlled at 0.05 level.

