### 8.1.1 Technical Computation Details for Primary Efficacy Analysis

The primary hypothesis is that the mean changes from baseline to Week 8 in both coprimary endpoints will differ from 0, separately. Each of the endpoints will be tested by fitting a MMRM analysis with an unstructured variance covariance structure at a two-sided significance level of 0.05 on OC dataset on Efficacy Sample. The model will include fixed effect terms for visit, baseline value, an interaction term of baseline value by visit, and trial center. The trial will be claimed positive if both p-values are less than 0.05. Therefore, the overall type I error is controlled at 0.05 level.

In case there is a convergence problem with MMRM model with the unstructured variance covariance matrix, the following structures other than unstructured will be used in order of 1) heterogeneous Toeplitz, 2) heterogeneous autoregressive of order 1, and 3) heterogeneous compound symmetry and the first (co)variance structure converging to the

best fit will be used as the primary analysis. If a structured covariance has to be used, the "sandwich" estimator of the standard error of the fixed effects parameters will be used in order to deal with possible model misspecification of the covariance matrix.

The SAS code for the PROC MIXED procedure to carry out the above MMRM analysis with an unstructured variance covariance structure is illustrated as follows:

where baseline is the last IDS-SR assessment total score at baseline.

[figure not shown]

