#### 8.2 Other Efficacy Endpoint Analysis

The other efficacy endpoints are as follows. All of them will be evaluated at a nominal 0.05 level (2-sided) without adjusting for multiplicity on Efficacy Sample:

[figure not shown]
- 1) Change from baseline to Weeks 2 and 4 in IDS-SR-10-engagement
- 2) Change from baseline to Weeks 2 and 4 in IDS-SR Total score
- 3) Change from baseline to Weeks 2, 4, and 8 in IDS-SR patient-selected engagement items
- 4) Change from baseline to Weeks 2, 4, and 8 in IDS-SR engagement items selected by both clinicians and patients.
- 5) Change from baseline to Weeks 2, 4, and 8 in CGI-S score
- 6) CGI-I score at Weeks 2, 4, and 8
- 7) Change from baseline to Weeks 4 and 8 in SDS Mean score and SDS individual item scores
- 8) Change from baseline to Weeks 4 and 8 in WHODAS 2.0 short form score.
- 9) Change from baseline to Weeks 2, 4, and 8 in PHQ-9 score
- 10) Change from baseline to Weeks 2, 4, and 8 in GAD-7 score
- 11) PGI-I score at each timepoint (ie, being measured weekly at home)

- 12) PGI-I response rate at each timepoint (ie, being measured weekly at home), where response is defined as a PGI-I score of 1 or 2 (very much improved or much improved)
- 13) Time to first PGI-S response, where response is defined as a reduction of 2 points in PGI-S score from baseline.

Endpoint (1) - (5), (7) - (10) will be analyzed by fitting the same MMRM model described in the primary analysis on OC dataset. Endpoints (6) and (11) will be analyzed using one-sample t-test on LOCF dataset, with the null hypothesis of no change in each of the endpoints. The point estimate with 95% CI will be provided for endpoint (12) using normal approximation on LOCF dataset. Endpoint (13) will be evaluated by time-to-event analysis with Kaplan-Meier curve on OC dataset. The time origin for measuring this event time is the date of the first dose of open-label brexpiprazole. The event date will be the date when a reduction of 2 points in PGI-S score from baseline is achieved.

Version Date: 29 Jun 2022

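### Does the success rule need a stated direction, and an explicit limit to change from baseline?

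*Protocol*

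**What the plan says.** The same rule stands in the Protocol synopsis (Statistical Methods), Protocol 9.4.1.1, Protocol 9.4.1.2 and SAP 8.1.1: "The trial will be claimed positive if both p-values are less than 0.05". Each place follows it with the statement "Therefore, the overall type I error is controlled at 0.05 level".

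Protocol 9.4.1.1 and SAP 8.1 list both endpoints as change from baseline to Week 8 (IDS-SR-10-engagement and IDS-SR Total score). Ahead of the rule, SAP 8.1.1 states: "The primary hypothesis is that the mean changes from baseline to Week 8 in both coprimary endpoints will differ from 0, separately". Protocol 9.4.1.1 has the same sentence. Testing is two-sided at 0.05 for each endpoint.

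Protocol 9.1 gives planned mean changes of -2.5 (SD 6.5) and -5 (SD 13.5), taken from brexpiprazole-plus-ADT arms of four previous trials, and it powers a difference from baseline. Protocol 9.3 anchors every item at 0 for best and 3 for worst.

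The aims are worded more broadly. The primary objective (Protocol 3) is "To prospectively characterize the effect of brexpiprazole on the concept of engagement". Protocol 4.2 says "the trial design is intended to assess the effect of adjunctive brexpiprazole on MDD patients when administered in a real-world setting". Protocol 9.1 says "This is a single-arm trial to assess the effect of brexpiprazole on patient engagement". All patients "will continue on the stable dose of ADT that they were taking at screening" (Protocol 4.1), and there is no comparator.

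For endpoints 6 and 11, SAP 8.2 specifies a test "with the null hypothesis of no change in each of the endpoints".

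**The concern.** Two things stand out on a first reading.

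- **Direction.** The rule looks only at p-values. Read literally, a trial in which both scores rose significantly would be positive, although a rise means more symptoms.
- **Attribution.** A positive trial with type I error controlled at 0.05, set beside an objective about the effect of brexpiprazole, could be taken as error control for a drug-effect claim. One open-label arm cannot supply that. Scores may also fall through natural course, continued ADT, expectation under open-label use of a self-report scale, or regression to the mean after entry at PHQ-9 of 15 or more. The planned changes are whole-arm changes, with no placebo response subtracted.

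If the second reading took hold, a result that needs no drug effect at all could be presented as evidence of one.

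**Working it through.** **Inputs.** SDs 6.5 and 13.5, planned changes -2.5 and -5, 100 completers, 25% early termination, two-sided 0.05 (Protocol 9.1 and 9.4.1.1). The documents give neither the correlation between the two change scores nor any non-drug change, so both are assumed below. One-sample t-tests on completers stand in for the planned MMRM.

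**1. The plan's own figures.** The noncentrality is (change/SD) × √n.
- Total: (5/13.5) × 10 = 3.70, power 95.6%. Stated: 95%.
- Engagement: (2.5/6.5) × 10 = 3.85, power 96.8%. Stated: at least 95%.
- Both: at least 0.956 + 0.968 - 1 = 0.924. Stated: at least 90%.
- Enrolment: 100/0.75 = 133.3, rounded up to 134. Stated: 134.

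All four reproduce.

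**2. The type I statement.** If at least one endpoint has no true change, the chance that both p-values fall below 0.05 cannot exceed that endpoint's own 0.05. The statement is therefore correct for the null of no change from baseline. If neither endpoint changes, both pass in 0.9% of trials at correlation 0.48 and 3.5% at 0.95. The lower value is 6.5/13.5, the correlation if the ten engagement items were uncorrelated with the other 18. The upper value is assumed.

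**3. The missing direction.** Double worsening with 100 completers:

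| True change (engagement / Total) | Both significantly worse |
|---|---|
| 0 / 0 | 0.4% to 1.8% |
| Total -2 | at most 0.03% |
| -2.5 / -5 (planned) | about 10⁻⁸ or less per endpoint |

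Requiring both changes to be below 0 as well leaves the chance of success at the planned changes at 93% to 95%, the same as without the condition. The only figure that moves is the maximum error for claiming improvement, which can be stated as 0.025 instead of 0.05.

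**4. Attribution.** The smallest significant mean change is t × SD/√n, with t(0.975, 99) = 1.984.
- Engagement: 1.984 × 6.5/10 = 1.29 points, 52% of the planned 2.5.
- Total: 1.984 × 13.5/10 = 2.68 points, 54% of the planned 5.

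Now suppose that all change is non-drug. The engagement items carry either half of the Total change (the planned ratio, 2.5/5) or 10/28 of it (an even spread over the 28 scored items). Simulated chance that both tests pass with 100 completers, correlation 0.48 to 0.95:

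| Assumed Total change | Half on engagement | 10/28 on engagement |
|---|---|---|
| -2 | 17% to 28% | 11% to 19% |
| -3 | 45% to 56% | 29% to 37% |
| -4 | 75% to 82% | 54% to 59% |

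These are not error rates of any rule in the plan. In every row scores have truly changed from baseline, so rejecting the stated null is correct. The figures are power to detect that change. They would count as false claims only if the plan said that success establishes a drug effect, and its hypothesis does not say that.

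**5. The passages side by side.** In Protocol 9.4.1.1 and SAP 8.1.1, the endpoint definition, the differs-from-0 hypothesis, the rule and the type I sentence come in sequence. Only Protocol 9.4.1.2 gives the rule without the hypothesis, and it directly follows the subsection that contains it. SAP 8.2 spells out a null for CGI-I and PGI-I. Those are improvement ratings, not changes from baseline, so its wording is no model for the co-primaries and does not show that they lack a null.

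**The case for a change.** The strongest case for a change is that a success rule should not rest on inference. Direction has to be read from planning values and item anchors, and the drug-effect wording appears in the objective, the design rationale and the sample size section. The earlier engagement evidence in Protocol 2.4 was a comparison with adjunctive placebo, which this trial does not have. If the whole planned change were non-drug, the trial would still succeed at least 92% of the time. The wording could be fixed without touching the model or the sample size.

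Part of this stands. The sign condition is absent in all four places, and the objective's wording goes further than an uncontrolled change can show. But a two-sided test with direction read from the estimate is ordinary practice, and no analyst would report a double worsening on a depression scale as success. The design is also disclosed: Protocol 9.1 says single-arm in the same sentence as the effect wording, Protocol 6.3 says open-label, and Protocol 4.2 explains the design as a way to mimic Canadian practice. The 92% figure measures what any uncontrolled trial cannot separate, and rewording the rule would not separate it either.

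**Conclusion.** No change is needed. The missing direction is a drafting shortcut that any analyst fills the same way. Its largest effect is 0.4% to 1.8%, at exactly zero change and for correlations of 0.48 to 0.95. It has no effect on estimates, p-values, power or the 134 to be enrolled.

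The missing limit on interpretation is already supplied by the hypothesis, which defines success as both changes from baseline differing from 0. The type I statement is correct for that null. What remains is a point for reporting: the result is a change from baseline during open-label adjunctive brexpiprazole, and it should be described that way.

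The conclusion rests on the visible text. The SAS code in SAP 8.1.1 and any SAP section between 8.2 and 8.4 could not be read. The calculations use t-tests as an approximation to the MMRM.

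### If the unstructured MMRM fails to converge, the plan goes straight to restrictive covariances that can bias the Week 8 mean, and the sandwich standard error does not protect against this

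*Protocol*

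**What the plan says.** Protocol 4.1 sets the post-baseline schedule: "Patients will attend visits at Weeks 2, 4, and 8 during the open-label treatment phase". The three visits in the model are therefore separated by gaps of 2 and 4 weeks.

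Protocol 9.4.1.1 tests each co-primary endpoint with an MMRM using an unstructured covariance. If that fit has a convergence problem, "structures other than unstructured will be used in order of 1) heterogeneous Toeplitz, 2) heterogeneous autoregressive of order 1", followed by heterogeneous compound symmetry. SAP 8.1.1 gives the same sequence: "used in order of 1) heterogeneous Toeplitz, 2) heterogeneous autoregressive of order 1, and 3) heterogeneous compound symmetry". Any structured fit takes a sandwich standard error, "in order to deal with possible model misspecification of the covariance matrix". Neither text describes an attempt to rescue the unstructured fit before moving to the list. The SAP's illustrative SAS code is not reproduced in the available copy.

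The Week 8 result from this model decides the trial: "The trial will be claimed positive if both p-values are less than 0.05".

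**The concern.** Heterogeneous Toeplitz forces the Week 2–4 and Week 4–8 correlations to be equal. Heterogeneous AR(1) does the same, and also fixes the Week 2–8 correlation at the square of that value. If correlation fades with time, the Week 4–8 correlation should be the lower one, and both structures push it up towards the Week 2–4 value. Compound symmetry makes all three correlations equal.

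With complete data this would be mainly a standard-error problem. With dropout under MAR, the likelihood predicts a leaver's Week 8 value from earlier scores through the fitted covariance. If patients doing worse tend to leave and the fitted Week 4–8 correlation is too high, their poor Week 4 scores are carried forward too strongly, and the estimated mean improvement shrinks. A sandwich standard error leaves that estimate where it is.

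At stake are the two co-primary estimates whenever the fallback is used. The same model serves other endpoints, so those with three post-baseline visits (1–5, 9 and 10) share the issue. Endpoints 7 (SDS) and 8 (WHODAS) do not: they have only Weeks 4 and 8, and with two visits all these structures are the same three-parameter model.

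**Working it through.** **The plan's own figures.** For engagement, protocol 9.1 uses a change of −2.5 with SD 6.5. For Total it uses "a mean change of -5 (standard deviation = 13.5) in IDS-SR Total score from baseline to Week 8". Both rest on 100 completers. For a two-sided one-sample t-test at 0.05:

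- Total: noncentrality 5/13.5 × √100 = 3.70, power 95.6%. The protocol says the sample size "will yield 95% power to show a difference from baseline in IDS-SR Total score", which agrees.
- Engagement: 2.5/6.5 × √100 = 3.85, power 96.8%.
- Both: at least 95.6 + 96.8 − 100 = 92.4%, above the stated 90%.
- Enrolment: 100/0.75 = 133.3, hence 134.

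These figures are not in dispute. They give standard errors of 13.5/√100 = 1.35 (Total) and 6.5/√100 = 0.65 (engagement).

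**Inputs for the bias check.** The documents give the Week 8 SD (13.5), the early-termination rate (25%), MAR and the visit weeks. They do not give within-patient correlations or a dropout mechanism, so these are assumed: monotone dropout totalling 25%, with log-odds of leaving rising by 0, 0.7 or 1.5 per SD of the last observed change (worse patients leave). Every candidate structure has a separate variance at each visit and dropout is set per SD, so the assumed Week 2 and Week 4 SDs do not affect the Week 8 bias.

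**Method.** Maximum-likelihood fits, with visit means only, to 1,000,000 simulated patients per scenario. Bias is the fitted minus the true Week 8 mean change in IDS-SR Total. Positive means towards no improvement.

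| Correlation W2–4 / W4–8 / W2–8 | Slope per SD | Toeplitz | AR(1) | Comp. symmetry |
|---|---|---|---|---|
| any scenario | 0 | 0 | 0 | 0 |
| 0.75 / 0.65 / 0.55 | 0.7 | +0.14 | +0.06 | +0.25 |
| 0.80 / 0.64 / 0.51 (decay with time) | 0.7 | +0.22 | +0.23 | +0.38 |
| 0.80 / 0.64 / 0.51 | 1.5 | +0.42 | +0.43 | +0.69 |
| 0.70 / 0.70 / 0.55 (adjacent equal) | 1.5 | 0.00 | −0.13 | +0.19 |
| 0.60 / 0.75 / 0.45 (reversed) | 1.5 | −0.32 | −0.30 | −0.08 |

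The unstructured fit stayed within 0.02 points in every scenario. In an extreme case (0.85/0.50/0.40, slope 1.5) Toeplitz and AR(1) reached +0.88 and +1.04.

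**Engagement.** Bias scales with the Week 8 SD, so multiply by 6.5/13.5 = 0.481. In the decay scenario, 0.22 × 0.481 = 0.11 and 0.43 × 0.481 = 0.21 points.

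**Effect on the Total test.** Power is approximately Φ((5 − bias)/1.35 − 1.96), which is 95.9% with no bias.

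- Bias 0.22 (4.4% of the effect, 0.16 SE): Φ(4.78/1.35 − 1.96) = 94.3%.
- Bias 0.43 (8.6%, 0.32 SE): Φ(4.57/1.35 − 1.96) = 92.3%.
- Under a true zero change, two-sided error is 5.3% and 6.2% respectively, but the tail that would falsely show improvement falls from 2.5% to 1.7% and 1.1%.

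**How likely the fallback is.** In 5,000 simulated trials of 134 patients (monotone dropout, visit means only), the unstructured estimate existed and was positive definite every time. With 15 centres, baseline-by-visit terms and 5% intermittent gaps, 100 of 100 REML fits converged. The second set used a purpose-written optimiser, not SAS.

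**The case against.** The strongest reply is that this is an ordered, pre-specified contingency that will probably never run: six covariance parameters, three visits, about 134 patients. That stands, and it is why the point is minor.

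The size may also be overstated. Protocol 9.1's 25% is an early-termination rate, not the share of the Efficacy Sample lacking a Week 8 value. Under SAP 11.1 an assessment from Day 42 counts as Week 8, and patients with no post-baseline score leave the Efficacy Sample. With about 12% missing, the bias roughly halves. This stands too.

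A reader might infer that the fallback estimate is necessarily biased whenever patients drop out. The documents do not support that: bias also needs dropout that depends on observed scores and true correlations that break the imposed pattern, and they specify neither.

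A reader might also infer that Toeplitz and AR(1) should be replaced by structures that do not assume equal spacing. That is not supported. Compound symmetry makes no spacing assumption and was the worst structure in every decay scenario. ANTE(1) was close to unbiased under exponential decay, but off by −0.06 to −0.17 under slower decay, where AR(1) was off by +0.02 to +0.10. No structured choice is uniformly safer.

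Finally, the SAS code missing from the available SAP may already set starting values or scoring options. If so, part of the fix is in place, but the written rule should still say it.

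**Conclusion.** The point holds in conditional form. If the unstructured fit fails, the listed structures can bias the Week 8 mean under outcome-dependent dropout, and the sandwich estimator does not address that. For Toeplitz and AR(1) on IDS-SR Total, a plausible size is about 0.1–0.4 points, or 2–8% of the planned 5-point change (0.1/5 to 0.4/5). This rests on assumed correlations, dropout slopes and 25% monotone dropout.

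The direction is mostly towards no improvement, so the results do not support reading this as a route to a false claim of benefit. The sign reverses if the Week 4–8 correlation is the higher one. The planned sample size and power are unaffected unless the fallback is used. The severity is low, but an inexpensive improvement is available.

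**What to change.** Add one sentence to protocol 9.4.1.1 and SAP 8.1.1: if the unstructured fit does not converge, the same unstructured matrix is first refitted with a Cholesky parameterisation (for example TYPE=FA0(3) for three visits), Fisher scoring and/or improved starting values, and the structured list with the sandwich standard error is used only if all of these fail.

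The refits leave the pre-specified model unchanged, so where one succeeds the bias is avoided whatever the true correlations. The structured list can stay as a last resort.

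The cost is a sentence in each document and a SAS option, with no extra data or patients and no loss of power. The protocol change would go through the amendment process in protocol 10.4.
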